Abbreviated Title: Targeted Rx in Advanced NETs
Version Date: 01/15/2019

Abbreviated Title: Targeted Rx in Advanced NETs

CC Protocol: 15C0040 J

Version Date: 01/15/2019

NCT Number: NCT02315625

Title: A Phase II Trial of Mutation-Targeted Therapy with Sunitinib or Everolimus in Patients with Advanced Low-or Intermediate Grade Neuroendocrine Tumors of the Gastrointestinal Tract and Pancreas

NCI Principal Investigator: [name]
Surgical Oncology Program (SOP)
[name]
[name]
[name]
[contact]
Email: [contact]

Investigational Agents: None

Commercial Agents: Everolimus, Sunitinib

Précis

Background:

- Neuroendocrine tumors (NETs) of the gastrointestinal tract and pancreas are a rare and heterogeneous group of neoplasms with unique tumor biology, natural history, and clinical management issues.
- Most NETs are sporadic, but they can be part of familial cancer syndromes such as multiple endocrine neoplasia type 1 (MEN1), neurofibromatosis type 1 (NF1) or Von Hippel-Lindau (VHL) syndrome.
- Well-differentiated, low or intermediate grade NETs have a heterogeneous natural history.
- Surgery is the only curative treatment option in patients with localized early stage NETs.
- The optimal management strategy for patients with advanced NETs is unknown.
- The majority of NETs have somatic mutations in *MEN1* and *CDKN1B*, and genes involved in the *PI3K/AKT/mTOR* signaling pathway, and/or overexpression of growth factors and their receptors such as *VEGF*, *VEGFR*, *PDGF*, and *PDGFR* that can be targeted for therapy.
- Survival in patients with NETs and somatic mutations is better than patients with wildtype NETs.
- Sunitinib (multi-tyrosine kinase inhibitor) and everolimus (mTOR signaling pathway inhibitor) are currently approved for the treatment of progressive, unresectable, locally advanced or metastatic pancreatic NETs.
- However, mutation targeted therapy with sunitinib or everolimus has not been studied in this patient population.
- The present proposal aims to determine if mutation targeting therapy for patients with advanced low- or intermediate grade NETs is more effective than historically expected results.

Objectives:

- To determine the progression-free survival in patients with NETs of the gastrointestinal tract and pancreas treated with sunitinib or everolimus based on tumor genotyping.

Eligibility:

- Patients with:
 - progressive, histologically or cytologically diagnosed low or intermediate grade locally advanced or metastatic NETs.
 - Age \geq 18 years

Design:

- Phase II open labeled clinical trial.
- Tumor biopsy for tumor genotyping will be performed if the patient does not have archival tissue available and does not have MEN1, VHL or NF1.

- Patients with somatic or germline mutations in *MEN1/PDGFR/KIT/FMS*-like tyrosine kinase-3 will be treated with sunitinib (Arm 1).
- Patients with somatic/germline mutations in *NF1/PTEN/PI3K/AKT/mTOR/VHL* will be treated with everolimus (Arm 2).
- Patients with wildtype tumor will be treated with sunitinib (Arm 1).
- Patients who have disease-progression on either sunitinib or everolimus will cross-over to the other drug.
- Treatment will continue until disease progression, unacceptable toxicity, or consent withdrawal.
- Up to 120 patients will be accrued to the study. It is anticipated that 20-30 patients per year may enroll into this trial; thus, accrual may be completed in 4-5 years.

TABLE OF CONTENTS

PRÉCIS 2

TABLE OF CONTENTS..... 4

1 INTRODUCTION 8

 1.1 Study Objectives 8

 1.1.1 Primary Objective: 8

 1.1.2 Secondary Objectives: 8

 1.2 Background and Rationale..... 8

 1.2.1 Neuroendocrine tumors..... 8

 1.2.2 Everolimus 13

 1.2.3 Sunitinib..... 16

 1.2.4 Rationale 20

2 ELIGIBILITY ASSESSMENT AND ENROLLMENT..... 21

 2.1 Eligibility criteria..... 21

2.1.1 Inclusion Criteria 21

2.1.2 Exclusion Criteria 22

 2.2 Screening Evaluation 24

 2.3 Registration Procedures 25

 2.3.1 Treatment Assignment Procedures (**For registration purposes only**):..... 25

 2.4 Baseline Evaluation 25

3 STUDY IMPLEMENTATION 26

 3.1 Study Design..... 26

 3.1.1 Cross-over..... 26

 3.1.2 Long term follow up 27

 3.2 Study Drug Administration..... 28

 3.2.1 Sunitinib Treatment and dose 28

 3.2.2 Everolimus Treatment and dose..... 29

 3.2.3 CCR Self-Administered Study Drugs Policy..... 30

 3.3 Dose Modifications/Dose Delay 30

 3.3.1 Sunitinib..... 30

 3.3.2 Everolimus 35

 3.4 Study Calendar..... 39

 3.5 Criteria for Removal from Protocol Therapy and Off Study Criteria..... 42

 3.5.1 Criteria for removal from protocol therapy 42

 3.5.2 Off-Study Criteria 42

 3.5.3 Off Protocol Therapy and Off Study Procedure 43

4 CONCOMITANT MEDICATIONS/MEASURES 43

 4.1 Supportive Care 43

 4.1.1 Management of Sunitinib-Induced Hypertension..... 43

4.1.2	Management of specific everolimus toxicities	45

1 INTRODUCTION

1.1 STUDY OBJECTIVES

1.1.1 Primary Objective:

- To determine the progression-free survival (PFS) on first-line therapy in patients with NETs of the gastrointestinal tract and pancreas treated with sunitinib or everolimus based on tumor genotyping.

1.1.2 Secondary Objectives:

- To determine overall response rate (ORR; i.e., sum of complete response [CR], partial response [PR], and stable disease [SD]) and duration of response
- To determine overall survival and median survival time (MST)
- To evaluate any relationship between tumor genotype, treatment and PFS
- Safety endpoints (i.e. AEs, clinical laboratory evaluations, ECGs, physical examination findings, and vital sign measurements).

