The highly vascular nature of NETs led to initial interest in investigating neoangiogenesis in NETs. A number of studies have found elevated expression of several cellular growth factors and their receptors in NETs; *VEGF*, *VEGF* receptor (*VEGFR*), platelet-derived growth factor (*PDGF*), *PDGF* receptor (*PDGFR*), and stem cell factor receptor (*c-KIT*), and epidermal growth factor receptor (*EGFR*)[62-65, 69, 70]. Many of these receptors with their respective growth factor ligands function as tyrosine kinases (TKs) directly and indirectly regulating tumor growth, survival and angiogenesis. The hypothesis that inhibiting these targets in concert will result in broad antitumor efficacy in patients with NETs has been studied in several clinical trials (**Table 2**).

Table 2. Phase II and III Trials in advanced NETs

Study tumor type and Regimen	Total No. of Patients	ORR (%)	Median PFS (months)	Median TTP (months)	Criteria	P
PNETs						
Moertel et al[35]	105					
Streptozocin + Doxorubicin		69		20.0	NS	.001
Streptozocin + Fluorouracil		45		6.9		
Raymond et al[53]	171					
Sunitinib		9		11.4	RECIST	< .001
Placebo		0		5.5		
Yao et al[55]	410					
Everolimus			11.0		RECIST	< .001
Placebo			4.6			
Carcinoid tumors						
Rinke et al[71]	90					
Octreotide LAR		2		14.3	WHO	< .001
Placebo		2		6.0		
Pavel et al[72]	429					
Everolimus + octreotide LAR			16.4		RECIST	.026
Placebo + octreotide LAR			11.3			
Kulke et al[63]						
Sunitinib	41	2.4		10.2	RECIST	

Abbreviations: PNETs, pancreatic neuroendocrine tumors; ORR, overall response rate; PFS, progression-free survival; TTP, time to progression; RECIST, Response Evaluation Criteria in Solid Tumors; LAR, long-acting release; NS, Nonstandard (includes computed tomography scan, radioisotope scan, physical exam, or hormonal response)

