1.2.3.2 Clinical Experience

1.2.3.2.1 Phase 1

In an early phase 1 study designed to investigate dosing regimen and scheduling (in human subjects, the results of clinical pharmacology studies demonstrate that C_{max} and area under the concentration-time curve (AUC) increased in a proportional manner after single doses of 50 to 350 mg as well as after multiple doses of 25-100 mg), 41 patients with a variety of advanced solid tumors received sunitinib administered on a schedule of 2 weeks of treatment followed by 2 weeks off (2/2 schedule) or 4 weeks on with 2 weeks off (4/2 schedule)[84]. Doses evaluated on the 2/2 schedule (n=23) included 50 mg every other day (n=3), 50 mg daily (n=15), or 75 mg daily (n=5); the 18 patients enrolled in the 4/2 schedule received 25 mg daily (n=3) or 50 mg daily (n=15). The most frequent adverse events (AEs) were constitutional (fatigue/asthenia), gastrointestinal (nausea, vomiting, diarrhea) and hematologic (neutropenia, thrombocytopenia). Most of the AEs were grade 1 or 2, although at 75 mg daily, grade 3 and 4 fatigue/asthenia were dose limiting but readily reversible on discontinuation of treatment. There were 4 partial responses (PRs) assessed by RECIST and 22 patients with stable disease (SD) among the 41 patients.

A phase 1 dose-escalation study in 28 patients with advanced tumors evaluated sunitinib doses of 30 mg/m² every other day, and doses of 30, 42, or 59 mg/m² daily on the 4/2 schedule[85]. Grade 3 fatigue and hypertension were dose limiting at 59 mg/m² as well as grade 2 bullous skin toxicity, and the MTD was defined as 42 mg/m² daily. Based on these and other reversible AEs in the 12 patients treated at the MTD, the recommended phase 2 dose on the 4/2 schedule was determined to be 50 mg/day. Responses determined by RECIST were seen in 6 of 23 evaluable patients: 3 in RCC, 1 in NET, 1 in GIST, and 1 in adenocarcinoma of unknown primary. Tumor responses in patients treated at higher doses were often associated with reduced intratumoral vascularization and central tumor necrosis, leading to organ perforation in one patient and fistula in another. These observations suggest the possible necessity for careful tumor density monitoring to detect early evidence of necrosis.

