1.2.3.2.2 Phase II and Phase III in NET

A phase II trial in patients with advanced NETs who received sunitinib demonstrated a median time to tumor progression of 7.7 and 10.2 months in patients with pancreatic NETs and carcinoid tumors, respectively[63]. A follow-up randomized, double-blind phase III trial comparing the response of 86 randomly selected patients given sunitinib with that of 85 patients on placebo demonstrated significant improvement in median PFS of patients on sunitinib (11.4 months versus 5.5 months)[53]. Moreover, patients treated with sunitinib showed early signs of an increase in overall survival[54]. Based on these findings sunitinib was approved by the FDA for the treatment of progressive, unresectable, locally advanced or metastatic PNETs. Unfortunately, none of these clinical trials evaluated what pathways or genes were altered in patient tumor samples and whether response to sunitinib was related to the tumor genotype.

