6.3 RESPONSE CRITERIA

For the purposes of this study, patients should be re-evaluated for response every 12 weeks.

Response and progression will be evaluated in this study using the international criteria proposed by the revised Response Evaluation Criteria in Solid Tumors (RECIST) guideline (version 1.1). Changes in the largest diameter (unidimensional measurement) of the tumor lesions and the shortest diameter in the case of malignant lymph nodes are used in the RECIST criteria.

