6.3.4.3 Evaluation of Best Overall Response

The best overall response is the best response recorded from the start of the treatment until disease progression/recurrence (taking as reference for progressive disease the smallest measurements recorded since the treatment started). The patient's best response assignment will depend on the achievement of both measurement and confirmation criteria.

For Patients with Measurable Disease (i.e., Target Disease)

Target Lesions	Non-Target Lesions	New Lesions	Overall Response	Best Overall Response when Confirmation is Required*
CR	CR	No	CR	≥4 wks. Confirmation**
CR	Non-CR/Non-PD	No	PR	≥4 wks. Confirmation**
CR	Not evaluated	No	PR	
PR	Non-CR/Non-PD/not evaluated	No	PR	
SD	Non-CR/Non-PD/not evaluated	No	SD	Documented at least once ≥4 wks. from baseline**
PD	Any	Yes or No	PD	no prior SD, PR or CR
Any	PD***	Yes or No	PD	
Any	Any	Yes	PD	

* See RECIST 1.1 manuscript for further details on what is evidence of a new lesion.
 
** Only for non-randomized trials with response as primary endpoint.
 
*** In exceptional circumstances, unequivocal progression in non-target lesions may be accepted as disease progression.
 
Note: Patients with a global deterioration of health status requiring discontinuation of treatment without objective evidence of disease progression at that time should be reported as “symptomatic deterioration.” Every effort should be made to document the objective progression even after discontinuation of treatment.
				

For Patients with Non-Measurable Disease (i.e., Non-Target Disease)

Non-Target Lesions	New Lesions	Overall Response
CR	No	CR
Non-CR/non-PD	No	Non-CR/non-PD*
Not all evaluated	No	not evaluated
Unequivocal PD	Yes or No	PD
Any	Yes	PD

* ‘Non-CR/non-PD’ is preferred over ‘stable disease’ for non-target disease since SD is increasingly used as an endpoint for assessment of efficacy in some trials so to assign this category when no lesions can be measured is not advised
		

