6.3.5 Duration of Response

Duration of overall response: The duration of overall response is measured from the time measurement criteria are met for CR or PR (whichever is first recorded) until the first date that recurrent or progressive disease is objectively documented (taking as reference for progressive disease the smallest measurements recorded since the treatment started).

The duration of overall CR is measured from the time measurement criteria are first met for CR until the first date that progressive disease is objectively documented.

Duration of stable disease: Stable disease is measured from the start of the treatment until the criteria for progression are met, taking as reference the smallest measurements recorded since the treatment started, including the baseline measurements.

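### Section 1.1.2 counts stable disease in the overall response rate, so the endpoint is a disease-control rate under the name of a response rate

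*Combined protocol and SAP*

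**What the plan says.** - **Section 1.1.2** lists as a secondary objective "overall response rate (ORR; i.e., sum of complete response [CR], partial response [PR], and stable disease [SD"]), followed in the same bullet by duration of response.
- **Section 6.3.5** gives two different clocks. For overall response: "The duration of overall response is measured from the time measurement criteria are met for CR or PR". For stable disease: "Stable disease is measured from the start of the treatment until the criteria for progression are met".
- **Section 1.2.1, Table 2** uses the same abbreviation ("ORR, overall response rate; PFS, progression-free survival") without listing its components. It prints ORRs of 9% for sunitinib and 0% for placebo in pancreatic NETs, and 2.4% for sunitinib in carcinoid tumors. It gives no ORR for everolimus.
- **Section 6.3** sets the assessment interval: "patients should be re-evaluated for response every 12 weeks". Section 3.1.2 and the study calendar in Section 3.4 say every 3 months, and Section 3.4 allows visits up to 7 days early or late.
- **Section 6.3.4.3** asks for stable disease to be documented at least 4 weeks from baseline, but footnotes that rule: "Only for non-randomized trials with response as primary endpoint". The primary endpoint here is PFS.
- **Section 6.3.1** limits evaluability for response to patients whose disease has been re-evaluated. **Section 8** evaluates response in all treated patients, descriptively, and does not say which categories count as a response.

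**The concern.** A response rate is normally read as tumor shrinkage. Under Section 1.1.2 a patient whose tumor has neither shrunk enough for PR nor grown enough for PD is a responder. Three things follow.

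First, the two halves of one objective use different patients. Someone whose best result is stable disease counts in the rate, but duration of overall response in Section 6.3.5 gives that person no start date.

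Second, the endpoint shares its name with the published ORRs in Table 2 but is on another scale. A reader could take a figure above 80% as a large gain over 9%.

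Third, a single scan without progression is enough to count. The rate therefore largely restates progression-free status at the first scan and adds little to the primary PFS endpoint.

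The mismatch between Sections 6.3.1 and 8 also leaves the denominator unsettled.

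**Working it through.** The plan gives no target, power or sample size for response, so there is no planned figure to reproduce. The check asks whether Table 2's ORRs could include stable disease, and how large the Section 1.1.2 rate would be.

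**Inputs**
- Sunitinib trial in pancreatic NETs: ORR 9% versus 0% (Table 2). Section 1.2.3.2.2 reports "significant improvement in median PFS of patients on sunitinib (11.4 months versus 5.5 months"). Table 2 prints the same two medians in its time-to-progression column.
- Design medians of 11 and 18 months, and 44 patients per arm (Section 8).
- First scan at 12 weeks (Section 6.3) or 3 months (Sections 3.1.2 and 3.4).

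**Step 1: bound without a distribution.** A median of 5.5 months means that S(5.5) is about 50%. Since S(3) ≥ S(5.5), at least about half of the placebo patients had not progressed at 3 months. If Table 2 counted stable disease, the placebo ORR would be about 50% or more. It is 0%, so stable disease is excluded.

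**Step 2: size at the first scan.** Assume that every patient alive without progression at the first scan is classified SD or better. With exponential PFS, S(t) = 0.5^(t/median).

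| Setting | Median (months) | Printed ORR | t = 3 months | t = 12 weeks (84/30.4375 = 2.76 months) |
|---|---|---|---|---|
| Placebo, pancreatic NET | 5.5 | 0% | 0.5^(3/5.5) = 68.5% | 70.6% |
| Sunitinib, pancreatic NET | 11.4 | 9% | 0.5^(3/11.4) = 83.3% | 84.6% |
| Design null | 11 | none | 0.5^(3/11) = 82.8% | 84.0% |
| Design alternative | 18 | none | 0.5^(3/18) = 89.1% | 89.9% |

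Per arm at 3 months this is 44 × 0.828 = 36.4 and 44 × 0.891 = 39.2 patients. An ORR of 9% would be 44 × 0.09 = 4.0 patients.

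**Step 3: sensitivity to shape.** With a Weibull curve, S(3) = 0.5^((3/median)^k). For k = 0.8 and k = 1.5:
- median 5.5: 65.3% and 75.6%
- median 11.4: 78.8% and 91.1%

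**Step 4: the same gap in observed counts.** For one phase 1 sunitinib study, the protocol states: "There were 4 partial responses (PRs) assessed by RECIST and 22 patients with stable disease (SD) among the 41 patients". CR+PR is 4/41 = 9.8%. With stable disease added it is (4 + 22)/41 = 26/41 = 63.4%. These were mixed solid tumors, so this only illustrates the effect of the definition.

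**Step 5: minimum time for stable disease.** The 4-week rule does not apply to this trial by its own footnote. If it did, a first scan at about 12 weeks would meet it automatically, so it excludes nobody assessed on schedule.

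**The case against.** The strongest case against is that the definition is explicit. Section 1.1.2 spells out its components, and Section 3.1.2 also puts CR, PR and SD in parentheses after response to treatment. Section 6.3.5 defines durations, not a rate, and does give stable disease a duration of its own. Reporting disease control is also reasonable in tumors that the protocol calls relatively indolent. Section 8 compares only PFS with historical results, so setting response beside Table 2 is something a reader might do, not something the plan does.

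Part of this stands. Stable disease is worth reporting, and the SD-inclusive rate should be kept under an accurate name. The comparison with Table 2 is a risk of misreading, not a planned analysis. The scan schedule, with its 7-day window, implies a minimum of about 11 weeks for stable disease on a scheduled scan, but the plan does not state it.

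The rest does not remove the defect. An explicit definition still leaves the rate and the duration of overall response covering different patients. Section 3.1.2 can be read as listing the categories assessed short of progression; read as a definition, it would only show that the word is used in two ways. Section 3.3.1 refers to patients on treatment who have no RECIST response, a group that would be nearly empty of non-progressors if stable disease were a response (cited for usage only).

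On the arithmetic, 12 weeks instead of 3 months moves the results by about 1 to 2 points. A median estimated with censoring is not a raw proportion, so the 50% bound is approximate. Neither closes a gap from 0%.

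**Conclusion.** The concern holds. The endpoint in Section 1.1.2 is a disease-control rate labelled as a response rate. It does not match the duration of overall response in Section 6.3.5, and it is on a different scale from the sunitinib ORRs in Table 2. At the design medians it would come out at about 83% to 90%, against published sunitinib ORRs of 9% and 2.4%.

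That Table 2 excludes stable disease is inferred from its ORR and median figures, because the table does not define ORR. The inference rests on the RECIST sunitinib trial and its placebo arm, not on the streptozocin trial, which used nonstandard criteria. The percentages assume exponential PFS, or Weibull where stated, and that all non-progressors are assessed at the first scan. Patients never assessed would lower the rate when all treated patients are the denominator.

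The consequence is limited. Response is secondary and descriptive, and the PFS test, its sample size and its error rate are untouched. It should be corrected before results are reported.

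**What to change.** 1. In Section 1.1.2, define ORR as the proportion of patients with a best overall response of CR or PR by RECIST 1.1. Duration of response then matches Section 6.3.5 as it stands.
2. Report CR+PR+SD separately as disease control rate, with duration of stable disease as in Section 6.3.5. State the minimum time from start of treatment for stable disease to count.
3. In the response sentence of Section 8, keep all treated patients as the denominator, name the two rates, and count patients without a post-baseline assessment as non-responders. Reconcile the evaluability wording in Section 6.3.1 with this.
4. Section 3.1.2 can stay as it is, because it does no harm once Section 1.1.2 defines the endpoint.

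The cost is a few sentences in Sections 1.1.2, 6.3.1 and 8. No new data are needed, because CR, PR and SD are already classified separately. The reported ORR will be lower.

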1.2 BACKGROUND AND RATIONALE

1.2.1 Neuroendocrine tumors

Neuroendocrine tumors (NETs) of the gastrointestinal tract and pancreas are a rare and heterogeneous, but clinically important group of neoplasms with unique tumor biology, natural history, and clinical management issues[1-4]. NETs arise in the disseminated neuroendocrine cells of the gastrointestinal tract (GI) mucosa (also called “carcinoids”) and the pancreatic islet cells. Approximately 85% of NETs are sporadic and the remainder occur as part of familial cancer syndromes including multiple endocrine neoplasia-type 1 (MEN1), von Hippel–Lindau disease (VHL), von Recklinghausen’s disease (neurofibromatosis 1, NF-1), and tuberous sclerosis (TS)[5-9].

Neuroendocrine cells are one of the largest group of hormone-producing cells in the body. At least 13 distinct gut neuroendocrine cells exist, all of which may oversecrete various bioactive peptides or amines including serotonin, somatostatin, histamine, and gastrin, which can result in significant morbidity and mortality. Up to 20% of patients with NETs may develop carcinoid syndrome associated with flushing, abdominal pain, diarrhea, bronchoconstriction, and carcinoid heart disease[10].

A unique feature of most NETs is the expression of somatostatin receptors (SSTR) by the tumor cells. There are five different SSTR subtypes; more than 80% of NETs of both the GI tract and pancreas express multiple subtypes, with a predominance of receptor subtypes 2 and 5[11-14]. Somatostatin is an endogenous SSTR agonist which inhibits the secretion of a broad range of hormones from the endocrine system, including serotonin, insulin, glucagon, and gastrin[15]. Somatostatin analogs have limited clinical use due to its short half-life (<3 min); however, long-acting somatostatin analogues play a central role in the treatment of hormonal symptoms produced by NETs but do not have significant antitumor activity[13, 16].

Epidemiology

The annual incidence of NETs has been increasing in the United States and worldwide[2, 7, 17-20]. Whereas early studies have reported incidences of < 1 per 100,000 persons per year[21-23], recent age-adjusted epidemiologic studies have shown a significant, more than five-fold, increase in NETs incidence from 1973 to 2005[7, 18-20, 24]. Based on data from the National Cancer Institute’s Surveillance, Epidemiology and End Results (SEER) cancer registry, the annual incidence of NETs was estimated to be 7.8 per 100,000 persons in 2013[7]. The prevalence of NETs has been estimated as 35 per 100,000 and may be considerably higher if clinically “silent” tumors are included[25].

Classification

NETs are generally classified into functioning (hormone hypersecreting) or nonfunctioning (clinically “silent”) tumors, based on their ability to produce hormone-associated symptoms. However, other classification systems with many common themes, such as the distinction of well-differentiated (low and intermediate-grade) from poorly differentiated (high-grade) NETs and the prognostic significance of proliferative rate index have been used over the past 5 decades (Table 1). In general, well-differentiated, low or intermediate grade NETs have a relatively indolent behavior with slow progression but poorly differentiated tumors may exhibit highly aggressive behavior with a rapid metastatic spread that is clinically indistinguishable from pancreatic adenocarcinoma or small-cell lung cancer[5, 7, 26]. Fortunately, poorly differentiated tumors account for only a small subset of all NETs.

Recent large, epidemiologic studies have shown that majority of NETs (60-90%) are clinically non-functioning, well-differentiated, slow-growing neoplasms diagnosed, in most instances, incidentally during an unrelated procedure[2, 6, 10, 13, 27-29]. As a result of this insidious biological behavior, many patients with NETs have advanced disease at diagnosis, with regional or distant metastasis observed in more than 50% of patients[13, 20].

Table 1: Nomenclature and Classification of Neuroendocrine Tumors

Differentiation & Grade	Mitotic Count (/10 HPF) ^a	Ki-67 Index (%) ^b	Traditional Classification	ENETS/WHO Classification	Moran et al[30]
Well differentiated					
Low grade (grade 1)	< 2	≤ 2	Carcinoid, islet cell, PNET	Neuroendocrine tumor, grade 1	Neuroendocrine carcinoma, grade 1
Intermediate grade (grade 2)	2-20	3-20	Carcinoid, atypical carcinoid ^c , islet cell, PNET	Neuroendocrine tumor, grade 2	Neuroendocrine carcinoma, grade 2
Poorly differentiated					
High grade (grade 3)	> 20	> 20	Small-cell carcinoma	Neuroendocrine carcinoma, grade 3, small cell	Neuroendocrine carcinoma, grade 3, small cell
			Large-cell neuroendocrine carcinoma	Neuroendocrine carcinoma, grade 3, large cell	Neuroendocrine carcinoma, grade 3, large cell

Abbreviations: HPF, high-power field; ENETS, European Neuroendocrine Tumor Society; PNET, pancreatic neuroendocrine tumor.

a HPF = 2 mm²; at least 40 fields (at ×40 magnification) were evaluated in areas of highest mitotic density. Cutoff values were taken from American Joint Committee on Cancer staging system (seventh edition).

b Ki67/MIB1 antibody; percentage of 2,000 tumor cells in areas of highest nuclear labeling. Cutoff values were taken from American Joint Committee on Cancer staging system (seventh edition).

c The term atypical carcinoid only applies to intermediate-grade neuroendocrine tumor of the lung.

Prognosis

Even though there has been a significant improvement in the diagnosis and management of NETs, no significant change in survival has been observed over the last 30 years[6, 7]. Reported survival times for patients with advanced NETs in population-based and institutional series are highly variable likely due to variability in tumor biology, classification, treatment modalities, and patient selection. According to data from the SEER database, the median overall survival (OS) for patients with metastatic NETs was two years[20], whereas in a large institutional database, the median OS for a similar group of patients was 5.8 years[31]. According to the European Neuroendocrine Tumor Society (ENETS) consensus statement, the median OS of nonfunctional NETs was 38 months with a 5-year survival rate of 43%[32].

Management of advanced NETs

Advanced NETs are characterized by local invasion, and regional and distant metastases. While the treatment of localized NETs is surgical resection, a variety of therapeutic options are available for patients with advanced NETs. These include medical control of excess hormone levels and associated symptoms, cytoreductive surgery for patients with advanced disease, radioembolization, chemoembolization, systemic chemotherapy, interferon, long-acting somatostatin analogs, receptor-targeted radionuclide therapy, and or liver transplantation[33-36]. When to apply a given option, what combination therapeutic approach should be used, how long treatment should be continued, and in what subgroup of patients a particular treatment option should be used is unclear and controversial[37].

[figure not shown]
When feasible, aggressive surgical resection has been associated with the best symptom-free and long-term survival results in patients with advanced NETs[6, 38-46]. Despite the lack of randomized control data, a recent consensus statement from the ENETS emphasized that resection should be the first-line treatment option for patients with advanced NETs if up to 90% of the disease burden is resectable[47]. However, only 5% to 20% of patients with advanced NETs meet this “conventional” criterion[43, 48]. Furthermore, a significant number of patients undergoing debulking surgery will have residual disease and recurrence rates are high[49]. Thus, it is becoming increasingly clear that combination (surgical and medical) therapeutic strategies to improve the outcomes of patients with advanced NETs need to be explored.

Mutation-targeted therapy

Our understanding of the genetic changes associated with sporadic and familial NETs has improved considerably over the last 3 decades. Driver oncogene and tumor suppressor genes have been identified in most NETs[50-56]. Overall, the majority of NETs will have somatic mutations in *MEN1*, the phosphatidylinositol 3-kinase (*PI3K*)/*AKT*/ mammalian target of rapamycin (*mTOR*) signaling pathway[20, 57-61], and or overexpression of growth factors and their receptor such as vascular endothelial growth factor (*VEGF*), *VEGF* receptor (*VEGFR*), platelet-derived growth factor (*PDGF*), and *PDGF* receptor (*PDGFR*) (**Figure 1**)[62-65]. The most common mutations (somatic and germline for familial cancer syndromes) are in *MEN1*,

VHL, *DAX*, *ATRX*, *TP53* and *CDKN1B*. These mutations are present in 87% of pancreatic neuroendocrine tumors and in 60% of gastrointestinal neuroendocrine tumors.

Figure 1. Signaling pathways commonly activated in NETs.

mTOR pathway in NETs

Several studies, using whole exome-sequencing and expression profiling, have consistently identified somatic mutations implicating the *mTOR* pathway as a common event in NETs (Figure 1)[57-59, 61, 63]. The *mTOR* pathway has a central role in cancer cell growth, proliferation, differentiation, and apoptosis. Tuberous sclerosis 2 (*TSC2*), phosphatase and tensin homolog (*PTEN*), *PIK3CA*, and fibroblast growth factor 13 (*FGF13*) are among the key modulators of the *mTOR* pathway[52, 56]. Several studies of global gene expression profiling in a large panel of pancreatic NETs showed that *TSC2* gene and *PTEN* gene were downregulated in most tumors, and their low expression was significantly associated with shorter disease-free and overall survival[59, 66]. In addition, expression of *FGF13* was significantly associated with liver metastasis and shorter disease-free survival[59, 66]. A recent whole-exome sequencing study also revealed the presence of somatic mutations in *MEN1*, *DAXX*, *ATRX*, *TSC2*, *PTEN*, and *PIK3CA* genes in the majority of sporadic pancreatic NETs[58]. Moreover, the presence of these mutations was associated with better survival when compared to patients with NETs, which had wild type *MEN1*, and/or *DAXX/ATRX*[58].

Activation of the *mTOR* pathway has also been implicated in several familial cancer syndromes (TS, NF-1, and VHL) associated with the development of NETs[20, 51, 59, 66-68]. Findings of these and other studies further support the critical role of the *mTOR* pathway in NETs and adds to the wealth of data that has spurred the clinical development of mTOR inhibitors as a treatment option for patients with advanced NETs (**Table 2**).

Key drivers of angiogenesis: growth factors and their receptors in NETs

The highly vascular nature of NETs led to initial interest in investigating neoangiogenesis in NETs. A number of studies have found elevated expression of several cellular growth factors and their receptors in NETs; *VEGF*, *VEGF* receptor (*VEGFR*), platelet-derived growth factor (*PDGF*), *PDGF* receptor (*PDGFR*), and stem cell factor receptor (*c-KIT*), and epidermal growth factor receptor (*EGFR*)[62-65, 69, 70]. Many of these receptors with their respective growth factor ligands function as tyrosine kinases (TKs) directly and indirectly regulating tumor growth, survival and angiogenesis. The hypothesis that inhibiting these targets in concert will result in broad antitumor efficacy in patients with NETs has been studied in several clinical trials (**Table 2**).

Table 2. Phase II and III Trials in advanced NETs

Study tumor type and Regimen	Total No. of Patients	ORR (%)	Median PFS (months)	Median TTP (months)	Criteria	P
PNETs						
Moertel et al[35]	105					
Streptozocin + Doxorubicin		69		20.0	NS	.001
Streptozocin + Fluorouracil		45		6.9		
Raymond et al[53]	171					
Sunitinib		9		11.4	RECIST	< .001
Placebo		0		5.5		
Yao et al[55]	410					
Everolimus			11.0		RECIST	< .001
Placebo			4.6			
Carcinoid tumors						
Rinke et al[71]	90					
Octreotide LAR		2		14.3	WHO	< .001
Placebo		2		6.0		
Pavel et al[72]	429					
Everolimus + octreotide LAR			16.4		RECIST	.026
Placebo + octreotide LAR			11.3			
Kulke et al[63]						
Sunitinib	41	2.4		10.2	RECIST	

Abbreviations: PNETs, pancreatic neuroendocrine tumors; ORR, overall response rate; PFS, progression-free survival; TTP, time to progression; RECIST, Response Evaluation Criteria in Solid Tumors; LAR, long-acting release; NS, Nonstandard (includes computed tomography scan, radioisotope scan, physical exam, or hormonal response)

